 VO_2 : Prior to our pilot study, there was no data on the effect of thiamine on VO_2 in hospitalized patients. We have therefore relied on our pilot data for the sample size calculation. In critically ill patients with preserved cardiac index (>2.4L/min/m²), the average increase in VO_2 after thiamine administration was 35mL/min. Using the average change in VO_2 of 35mL/min and the average standard deviation of 45mL/min, we will need to enroll 28 patients in each arm to achieve a power of 0.8 with a Type I error of 0.05. We have chosen to enroll 30 in each arm to allow some room for drop out.

Statistical Analysis General Principles

The statistical analyses and reporting will adhere to the CONSORT guidelines. All tests will be two-sided, a p-value <0.05 will be considered significant, and all confidence intervals will have 95% coverage. All analyses will be conducted on a modified intention-to-treat basis only including participants receiving at least the first dose of the study medication. In a double-blind trial, this approach is unbiased while increasing precision. Analyses will not be adjusted for covariates unless there are significant arm differences in baseline characteristics.

Baseline Characteristics

A description of the baseline characteristics will be presented by treatment arm. Categorical variables will be summarized by frequencies and percentages. Percentages will be calculated according to the number of patients for whom data are available. Continuous variables will be summarized using mean+/-standard deviation or median (interquartile range) based on the distribution of the data.

Analysis of Primary Outcome

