Prior to unblinding or analysis, oxygen consumption data will be cleaned using an algorithm designed by our research team in R version 4.1.1 (R Foundation for Statistical Computing, Vienna, Austria). This automated algorithm excludes VO₂ data (and the corresponding value for carbon dioxide production, or VCO₂) if one or more of the following criteria is met: all values recorded in the 10 min following a change in FiO₂ of 10%, all values recorded while FiO₂ is >61% (61% used in order to capture all situations when the ventilator is set for an FiO₂ of 60% or less, as the monitor reports this number to two decimal places and a set number of 60% may be recorded as 60.54%), all values deviating 15% or more from the mean of the previous five values and the next five values (i.e, deviating 15% from the mean of the ten neighboring data points), and all VO₂ values out of physiologic range unless these are persistent for more than 30 minutes, as these measurements are considered artifacts. Values that will be considered out of physiologic range are VO₂<80 mL/kg/min or VO₂>800 mL/kg/min. We allow these values if they persist for at least 30 min and if they are not excluded per the algorithm for other reasons, as critically ill post-arrest patients can sometimes have values well outside of standard normal range, due to temperature, medication use such as sedatives and neuromuscular blockade and/or alterations in metabolic function. The respiratory quotient (RQ) is calculated as the ratio of VCO₂/VO₂ at each time point. After data is run through the algorithm and still prior to unblinding, there is a final visual review of a graphical print-out of all data points for each patient to provide a secondary confirmation that values were kept or dropped appropriately.

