To investigate the association between treatment and gas metabolism data (VO₂, VCO₂ and RQ) in the first 48 hours after ROSC, we will compare the area under the curve (AUC) for each oxygen consumption variable between the treatment arms. The AUCs for the oxygen consumption variables are influenced by the number of minutes of data available, which varies between patients. To account for this, AUCs for each patient will be adjusted by dividing by the number of minutes of oxygen consumption data available for that patient. Additionally, the AUCs for the VO₂ and VCO₂ variables are influenced by the weight of the patient, and thus will also be adjusted by dividing by the bodyweight of the patient, in kilograms. The median AUCs will be compared between treatment groups using the univariate Wilcoxon rank-sum test. To

control for the known effect of temperature on oxygen consumption, we will use quantile regression to compare median AUCs between patients using the treatment assignment as the predictor and average temperature as a covariate. To examine the association between treatment and the VO₂:Lactate Ratio, we will use a linear quantile mixed model (LQMM) with the VO₂:Lactate Ratio as the outcome variable, treatment as the predictor variable and temperature as the covariate. To account for clustering of VO₂:Lactate Ratio and temperature measurements within patients, we will add a random intercept for each patient to the LQMM. We will not control for vasopressor use or sedation in the above analyses unless use of these agents is significantly imbalanced between arms.

Pyruvate dehydrogenase (PDH), creatinine, SOFA score, and cellular oxygen consumption rate levels over 48 hours

To test change over time, we will compare repeated measures of each outcome listed above at each time point (0h, 24h, 48h) between arms using a linear mixed-effects model with an independent variance—covariance matrix to account for the correlation of within-patient repeated measures. Covariates in the model include treatment arm, time, and the interaction between treatment arm and time. Linear contrasts will be used to estimate the mean difference between treatment arms for each time point. To test for a difference in absolute values between arms, we will compare means or medians, as appropriate, using either a Student's t-test or a Wilcoxon rank-sum test, respectively, at 24 and 48 hours.

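### The physiologic-range limits in the VO₂ cleaning rule carry the wrong unit: in mL/kg/min they put essentially every adult reading out of range, whereas the rest of the plan implies mL/min

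*Combined protocol and SAP*

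**What the plan says.** The section on change in VO₂ over 48 hours describes an automated R algorithm that removes a VO₂ value, with its VCO₂ value, "if one or more of the following criteria is met". There are four criteria:

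- a recent FiO₂ change ("all values recorded in the 10 min following a change in FiO₂ of 10" percent);
- FiO₂ above 61%;
- a value "deviating 15% from the mean of the ten neighboring data points";
- a value outside a physiologic range. The text says that values "out of physiologic range are VO₂<80 mL/kg/min or VO₂>800 mL/kg/min".

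Out-of-range values are kept if they persist for 30 minutes and "if they are not excluded per the algorithm for other reasons". A blinded visual review of each patient's plotted data follows.

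Two other places bear on the unit. The VO₂ paragraph of the sample size section reads "Using the average change in VO_2 of 35mL/min and the average standard deviation of 45mL/min". In the analysis that follows cleaning, each AUC is "adjusted by dividing by the number of minutes of oxygen consumption data available for that patient", and the VO₂ and VCO₂ AUCs "will also be adjusted by dividing by the bodyweight of the patient, in kilograms".

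**The concern.** The printed limits are per kilogram, but the numbers 80 and 800 look like whole-body limits in mL/min. The plan's only VO₂ figures with a unit, apart from these limits, are in mL/min. Dividing the AUC by weight after cleaning makes sense only if the cleaned series is not yet per kilogram; otherwise weight would be divided out twice.

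Of the four criteria, this is the only one that looks at the absolute level of VO₂. The FiO₂ criteria do not use VO₂, and the 15% criterion is relative to neighbouring points, so it cannot see the inside of a flat artifact. If the range limits do not work, nothing automated removes a short stretch of implausible but stable readings. The plan was posted as the prespecification, so a reader who programs it as printed would also get a different cleaned data set from the one presumably intended.

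**Working it through.** **Inputs.** From the plan: limits of 80 and 800, printed in mL/kg/min; VO₂ change of 35 and SD of 45 mL/min; 28 patients per arm; 80% power; two-sided 5% error. Assumed, because the plan gives no weights: adult bodyweight of 40 to 150 kg.

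**The plan's own VO₂ figure.** The normal approximation gives n per arm = 2 × (1.96 + 0.84)² × (45/35)² ≈ 26. A two-sample t-test gives 27, and dividing its unrounded 26.9 by 0.955 (Wilcoxon efficiency under normality) gives 28.2. The stated 28 is therefore reproduced to within two patients. The formula uses only the ratio 45/35, so this does not test the unit. It shows that the sample size does not depend on the cleaning limits.

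**Converting the limits.** Limit in mL/min = printed limit × weight. Per-kilogram value of 800 mL/min = 800 / weight.

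| Weight (kg) | Printed 80 mL/kg/min, in mL/min | Printed 800 mL/kg/min, in mL/min | 800 mL/min, in mL/kg/min |
|---|---|---|---|
| 40 | 3,200 | 32,000 | 20 |
| 70 | 5,600 | 56,000 | 11.4 |
| 150 | 12,000 | 120,000 | 5.3 |

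Even 800 mL/min in a 40 kg patient is 20 mL/kg/min, a quarter of the printed lower limit. Any reading up to 800 mL/min is therefore below the printed limit by a factor of at least four. This holds whichever unit the monitor exports.

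**What the printed rule would do.** With every reading out of range, all that is left of the criterion is the 30-minute exemption. It would keep long runs and drop short ones whatever their level.

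**Illustration, one patient.** Assumed: 70 kg, steady 250 mL/min, one 20-minute artifact run at 40 mL/min, and persistence judged on the raw series.

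- As printed, 250/70 = 3.6 and 40/70 = 0.6 mL/kg/min are both below 80. The whole recording is one persistent out-of-range run, so all of it is exempt and only the 15% criterion acts.
- That criterion removes the five artifact points at each edge. The fifth point in still has one neighbour at 250, so its neighbour mean is (250 + 9 × 40)/10 = 61, and 40 is 34% below that. From the sixth point on, all ten neighbours are 40 and nothing is removed.
- At 1 point per minute, 20 − 10 = 10 of 20 artifact points remain. At 15 per minute, 300 − 10 = 290 of 300 remain.
- With limits in mL/min, 40 is below 80 and the run is shorter than 30 minutes, so 0 remain.

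The 15% criterion also removes four valid points on each side of the run (8 in all). In a 240-minute recording at 1 per minute, 240 − 20 − 8 = 212 valid points and 10 artifact points are kept, so the mean shifts by −210 × 10/222 = −9.5 mL/min. At 15 per minute the shift is −210 × 290/3,582 = −17.0. Over 48 hours the shifts are −0.7 and −1.4.

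If persistence is instead judged after the other exclusions, 0 artifact points remain under either unit in this example.

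**The case against.** The strongest reply is that a unit label is not executed; the numbers are. If the exported column is in mL/min and the code compares it with 80 and 800, the cleaning is already right and only the text is wrong. Weight division comes later in the plan, which makes this likely. The code is not shown, so the reply can be neither confirmed nor excluded. It supports treating the point as a correction and a check rather than as a demonstrated fault in the algorithm.

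The blinded visual review also stands as a partial backstop. It would probably expose a gross failure, though the plan describes it as a secondary confirmation and gives it no numeric criterion.

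A reader might infer that the printed unit would delete most of the VO₂ data. The documents do not support this. Out of range does not mean removed, because persistent values are exempt. On the raw series, continuous valid data would be kept under either unit. If persistence is judged after the other exclusions, the answer turns on whether one removed point ends a run. With assumed independent noise, 48 hours of data and 1 point per minute:

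| Noise CV | Limits in mL/min | As printed, any gap ends a run | As printed, one-point gap allowed | As printed, two-point gap allowed |
|---|---|---|---|---|
| 8% | about 93% kept | about 34% | about 91% | about 93% |
| 10% | about 85% kept | about 5% | about 73% | about 84% |

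The plan gives neither the noise level, nor the rule order, nor the gap rule. No retention figure can be claimed.

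It would also be wrong to set the one-patient shifts in the illustration against the SD of 45 mL/min. The plan pairs that SD with a change in VO₂, whereas the analysis compares per-minute, per-kilogram AUCs by a rank test and median regression.

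**Conclusion.** The limits are wrong as written. The conclusion needs only an adult weight range and readings no higher than about 800 mL/min, and it has a margin of at least fourfold. That the intended unit is mL/min is an inference, though a firm one, from the sample size paragraph and the later division by weight.

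The consequence is conditional: it arises only if the printed unit is the one coded. In that case the range criterion could no longer tell artifact from real data. The illustration (10 of 20 or 290 of 300 artifact points left, against 0) shows the mechanism and is not an estimate for this trial, since the baseline, the artifact and the sampling rates are assumed.

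The reach is limited to the secondary VO₂, VCO₂, RQ and VO₂:lactate analyses and the VO₂ sub-analysis in thiamine-deficient patients. The primary lactate analysis and the sample size are unaffected. Severity: minor.

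**What to change.** Before unblinding:

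1. Confirm the unit in which the monitor exports VO₂ and the unit that the R cleaning code compares with 80 and 800.
2. Restate the limits as VO₂ below 80 or above 800 mL/min, applied to the raw data before any weight adjustment.
3. If the code uses the printed unit, correct it and rerun the cleaning.

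As a minor tidy-up, use one wording for the exemption, which now appears once as longer than 30 minutes and once as 30 minutes or longer. Add a sentence saying whether persistence is judged before or after the other exclusions, and whether a removed point ends a run.

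The cost is one unit correction, a sentence or two of text, and a check of the code and the export. No new data are needed.

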list of secondary outcomes) will be completed in the BIDMC Center for Resuscitation Science Lab.

VO₂ monitoring: All patients meeting criteria for metabolic data collection (FiO₂ 60% or less and positive end expiratory pressure (PEEP) 15cm H₂O or less) will be connected to the VO₂ monitor at enrollment or as soon as the ventilator criteria are met, if still within 48 hours of enrollment. The monitor is made by General Electric, monitor version B650 with gas exchange module, and attaches in-line to the ventilator tubing, between the endotracheal tube and the Y-connector. All connections and disconnections of the monitor will be done by a trained respiratory therapist, with study staff present at the bedside. The tubing is attached to sensors that collect data breath-by-breath and that data is continuously recorded while connected to a laptop with dedicated software for this purpose. At the end of the study protocol all data will be downloaded and stored in a secure CSV file.

Cerebral Performance Category (CPC) and Cerebral Performance Category-Extended (CPC-E) score assessments: CPC and CPC-E will be assessed just prior to hospital discharge, at 30 and 90 days. Research staff will approach patients for assessment of CPC-E prior to hospital discharge. The CPC-E includes several questions testing logical thinking, attention and memory. The outpatient portion, which will be assessed in addition to the inpatient portion after hospital discharge/at 30 and 90 days, also includes questions about functional status and return to work. The CPC score will also be assessed by research staff prior to discharge. Phone calls to the patient will be made at 30 and 90 days (if the patient is no longer in the hospital).

Outcome Measures

Primary Outcome: Lactate change

Note: At the time of trial start, the primary outcome was change in oxygen consumption (VO_2) over 48 hours and change in lactate was a secondary outcome. After the first year, however, the primary outcome was changed to lactate, and VO_2 was changed to secondary. This change was made due to too many patients not meeting the ventilator criteria to allow collection of VO_2 data for at least the initial several hours of the study protocol, and enrollments therefore lagging behind. This change in primary outcome was posted at that time on clinicaltrials.gov and was submitted and approved by our Internal Review Board (IRB).

Prespecified Secondary Outcomes:

- 1. Change in VO₂ over 48 hours

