- 2. Absolute level of lactate over 48 hours
- 3. absolute level and the change in oxygen consumption over 48 hours

- 4. absolute level and the change in pyruvate dehydrogenase (PDH) activity, quantity and specific activity over 48 hours
- 5. absolute level and change in creatinine over 48 hours
- 6. mortality (hospital discharge, 30 and 90 days)
- 7. Cerebral Performance Category (CPC) score (hospital discharge, 30 and 90 days)
- 8. Cerebral Performance Category-Extended (CPC-E) (hospital discharge, 30 and 90 days)
- 9. absolute level and the change in Sequential Organ Failure Assessment (SOFA) Score SOFA over 48 hours
- 10. renal failure during first 7 days following arrest
- 11. absolute level and change in cellular oxygen consumption rate over 48 hours

Sample Size Calculations:

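### Change in VO₂ is a listed secondary outcome and the basis of the VO₂ sample size, but the plan specifies only a comparison of time-averaged VO₂ level, with no pre-dose value and no account of when each patient was recorded

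*Combined protocol and SAP*

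**What the plan says.** All references are to the combined protocol and SAP.

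- **Prespecified Secondary Outcomes.** Item 1 is "Change in VO₂ over 48 hours". Item 3 is "absolute level and the change in oxygen consumption over 48 hours", so the plan treats level and change as two different things.
- **Sample Size Calculations, VO₂.** The calculation is made "Using the average change in VO_2 of 35mL/min and the average standard deviation of 45mL/min". It arrives at 28 per arm for a power of 0.8, raised to 30 for drop-out.
- **Analysis of Secondary Outcomes, Change in oxygen consumption (VO₂) over 48 hours.** The summary measure is an area under the curve, adjusted by "dividing by the number of minutes of oxygen consumption data available for that patient". VO₂ and VCO₂ are also divided by body weight. Then "The median AUCs will be compared between treatment groups using the univariate Wilcoxon rank-sum test". A quantile regression adds average temperature. The VO₂:lactate ratio goes into a linear quantile mixed model with "treatment as the predictor variable and temperature as the covariate", plus a random intercept per patient.
- **VO₂ monitoring.** A patient is connected at enrollment, or later once FiO₂ and PEEP allow it, provided this falls within 48 hours of enrollment. The note to the primary outcome says that VO₂ was demoted from primary because too many patients could not be recorded for at least the first several hours.
- **Additional Planned Analyses.** A sub-analysis of change in VO₂ in thiamine-deficient patients is named, without a method.

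**The concern.** An AUC divided by its own recorded minutes is a mean level. Nothing in the VO₂ section subtracts, adjusts for or even defines a pre-dose value, and nothing follows VO₂ over time by arm. Followed as written, the plan gives no estimate of secondary outcome 1, nor of the change half of outcome 3. The named sub-analysis inherits the same gap.

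Two further features weaken the level comparison itself. Minutes recorded between connection and the first dose count towards the treatment comparison, although they cannot carry a drug effect. And a patient recorded only in the first hours is set beside one recorded only late, as if the two averages described the same period.

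VO₂ is the outcome in the trial's title and was the primary outcome at the start, so readers will look for a clear answer on it. The primary lactate analysis is not affected.

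**Working it through.** **1. Outcomes against analyses**

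| Outcome | Method for change | Method for level |
|---|---|---|
| Lactate | Mixed model, arm × time | t-test or Wilcoxon at each time |
| PDH, creatinine, SOFA, cellular oxygen consumption | Mixed model, arm × time | t-test or Wilcoxon at each time |
| VO₂ | None specified | AUC per minute per kg |

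The plan has its own standard for outcomes listed as both level and change. VO₂ is the exception.

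**2. The VO₂ sample size**

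Inputs from the plan: difference 35 mL/min, SD 45 mL/min, two-sided 0.05, power 0.8, 1:1 allocation.

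- Normal approximation: n = 2 × [45 × (1.960 + 0.842) / 35]² = 25.9, so 26 per arm.
- Two-sample t-test: 26.9, so 27 per arm.
- With the usual Wilcoxon efficiency of 0.955: 26.9 / 0.955 = 28.2.

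The stated 28 is therefore reproduced closely. Power at 28 per arm is 81.5% by the t-test. The figure belongs to a change of 35 mL/min in absolute units, whereas the planned endpoint is a level per kilogram.

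**3. What a level comparison does to power**

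The documents give no within-patient correlation r for VO₂ and do not say whether 45 is the SD of change or of level. Assume that it is the SD of change.

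- SD of a single reading: s = 45 / √(2(1 − r)).
- SD of an average of many readings under constant correlation: approaches s × √r.
- SD after adjusting a single reading for a single baseline: s × √(1 − r²).

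Two-sample t power for 35 mL/min at 28 per arm:

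| r (assumed) | Single-reading SD | Power | SD of average | Power | Baseline-adjusted SD | Power |
|---|---|---|---|---|---|---|
| 0.3 | 38.0 | 92% | 20.8 | >99% | 36.3 | 94% |
| 0.5 | 45.0 | 82% | 31.8 | 98% | 39.0 | 91% |
| 0.6 | 50.3 | 73% | 39.0 | 91% | 40.2 | 89% |
| 0.7 | 58.1 | 60% | 48.6 | 75% | 41.5 | 87% |
| 0.8 | 71.2 | 44% | 63.6 | 52% | 42.7 | 85% |
| 0.9 | 100.6 | 25% | 95.5 | 27% | 43.9 | 84% |

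If 45 is instead the SD of level, a single-reading level comparison has about 82% power and nothing is lost. The averages assume many readings with constant correlation; short or strongly autocorrelated recordings would gain less. The table ignores weight scaling, which may remove some between-patient variation.

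**4. When, as opposed to how long**

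Illustration (assumed): VO₂ rises linearly by 35 mL/min over 48 hours in everyone, with no treatment effect. A patient recorded from hour s to 48 has a mean that exceeds the full-window mean by 35 × s / 96.

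- s = 12: 4.4 mL/min.
- s = 24: 8.8 mL/min.

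Dividing by minutes does not remove this shift. It is noise if start and stop times are alike in the two arms, and bias if they are not.

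**5. Window**

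The AUC text counts 48 hours from ROSC; the monitoring text counts from enrollment. The first dose may come up to 12 hours after ROSC. For such a patient the ROSC window holds only 48 − 12 = 36 post-dose hours, and any recording before the dose falls inside it.

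**6. VO₂:lactate ratio**

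Blood is drawn at 0, 6, 12, 24 and 48 hours, and the time-0 draw precedes study drug. The plan does not list the time points of the ratio. If a time-0 ratio is included, a model with treatment as a main effect and no time term averages it into the treatment effect.

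**The case against.** Randomization makes baseline VO₂ equal in expectation, so a difference in post-dose level targets the same treatment effect as a difference in change. This stands. A reader might infer that the plan cannot answer its VO₂ question at all; it can, as a difference in average level, and outcome 3 does list absolute level.

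A reader might also infer that the analysis is underpowered, or that differences between patients drown any within-patient change. The documents do not support this. The result depends on a correlation and on a meaning of the SD of 45 that they do not give. The single-reading calculation also overstates the SD of an endpoint that averages many minutes.

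A third tempting reading is that recording time is confounded with treatment. Unequal windows mainly add noise. Bias would need the time of meeting ventilator criteria, of extubation or of death to differ by arm, and nothing in the documents shows that it does.

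Lastly, pre-dose dilution may be small, because patients who start late have few or no pre-dose minutes. That is fair, and its size cannot be worked out from the documents.

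None of this supplies a method for change.

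**Conclusion.** The point holds as a mismatch between outcome and analysis. No analysis of change in VO₂ is specified, although change is secondary outcome 1, half of outcome 3, the basis of the VO₂ sample size and the subject of a named sub-analysis. The AUC comparison is a valid but different quantity. It lets pre-dose minutes in and ignores when recording took place; the VO₂:lactate model shares the missing time term.

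The gap itself follows from the text and needs no assumption. Its effect on precision cannot be fixed: on the assumptions of step 3 it runs from none to severe, so no power loss should be reported. What can be said is that, on the same single-reading footing, adjustment for baseline is at least as precise as the plain level comparison at every correlation shown. Since VO₂ is secondary, this should be corrected but does not threaten the primary conclusion.

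**What to change.** Before unblinding:

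1. Add a repeated-measures analysis of weight-adjusted VO₂ in the style already planned for lactate and PDH, or with the planned quantile mixed model. Include arm, time since first dose, arm-by-time and a patient random intercept. Enter pre-dose VO₂, where available, as the time-0 outcome, so that patients without it still contribute. State how the continuous recording is summarized into time intervals, and apply the same model to the sub-analysis in thiamine-deficient patients.
2. Restrict the AUC to post-dose minutes and label it as absolute level. State one 48-hour window, since the ROSC and enrollment versions differ.
3. Add time to the VO₂:lactate model, list its time points, and keep any pre-dose ratio out of the treatment effect.

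The cost is some extra modelling of data already recorded. Patients without a pre-dose recording add less to the change estimate. Recording that ends with extubation or death remains a missing-data limitation under the new model too, and should be reported by arm together with start times.

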Thiamine vs. Placebo to Increase Oxygen Consumption After Cardiac Arrest: Study protocol and statistical analysis plan

NCT02974257

Finalized and submitted to Clinicaltrials.gov: August 4, 2022

Principal Investigator and corresponding author: [name] [contact]

Introduction

The study protocol for Thiamine vs. Placebo to Increase Oxygen Consumption After Cardiac Arrest is summarized in the original posting for the trial on clinicaltrials.gov, NCT02974257. Additional details on the protocol and the statistical analysis plan are included in this document, which is being submitted for posting prior to unblinding or initiation of any data analysis.

Methods

Trial Design:

This is a randomized, double-blind, placebo-controlled trial of high-dose intravenous thiamine to decrease lactate and increase global oxygen consumption (VO₂) in patients who achieve return of spontaneous circulation (ROSC) after an in-hospital cardiac arrest (IHCA).

Consent:

Eligible patients will be intubated and sedated at the time of eligibility. Therefore, the legally authorized representative (LAR) will be approached by the research team, and written informed consent will be obtained prior to beginning the study protocol. If patients improve to the point of being consentable, they will be approached for consent for continuing participation.

Intervention:

Thiamine 500mg in 100mL 0.9% saline IV every 12 hours for 48 hours, with initial dose given within 12 hours of ROSC. Control arm will receive 0.9% saline of the same volume and frequency.

Patient Population

Inclusion Criteria:

- Adult patient (age ≥ 18 years)
- Cardiac arrest occurring while admitted to the hospital, with sustained (>20 minutes) return of spontaneous circulation (ROSC)
- Mechanically ventilated at the time of enrollment
- Within 12 hours of cardiac arrest event

Exclusion Criteria:

• Clinical indication for thiamine administration (alcoholism, known or highly suspected deficiency) or treatment with thiamine beyond the amount found in a standard multivitamin within the last 10 days

- Comfort measures only or anticipated withdrawal of support within 24 hours
- Severe agitation
- Protected populations (pregnant women, prisoners)

Randomization and blinding

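### The adjusted VO₂ models add vasopressor and sedation use only on a significant imbalance, with no limit to pre-dose use, so part of a treatment effect could be adjusted away

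*Combined protocol and SAP*

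**What the plan says.** The section on change in oxygen consumption sets out three analyses.

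- Unadjusted, for VO₂, VCO₂ and RQ: "The median AUCs will be compared between treatment groups using the univariate Wilcoxon rank-sum test".
- Quantile regression of the same AUCs, "using the treatment assignment as the predictor and average temperature as a covariate".
- A linear quantile mixed model (LQMM) for the VO₂:lactate ratio, with treatment, temperature and a random patient intercept.

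It then adds: "We will not control for vasopressor use or sedation in the above analyses unless use of these agents is significantly imbalanced between arms". The sentence does not say whether use means any use, dose or duration, over what period it is counted, or which test decides.

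Three other statements bear on how to read it. The general principles already contain a baseline rule: "Analyses will not be adjusted for covariates unless there are significant arm differences in baseline characteristics". The outcome window is fixed in the VO₂ section: "in the first 48 hours after ROSC, we will compare the area under the curve (AUC) for each oxygen consumption variable between the treatment arms". Study drug is given "every 12 hours for 48 hours, with initial dose given within 12 hours of ROSC".

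**The concern.** Drug use counted after the first dose is a post-randomisation variable. If thiamine alters haemodynamics or the need for sedation, vasopressor and sedative use lies on the path from treatment to VO₂. Conditioning on it removes the part of the effect that travels along that path. It can also introduce bias through shared causes of drug use and VO₂, such as illness severity. The plan itself treats sedation as acting on the outcome: in the data-cleaning text it explains extreme values as "due to temperature, medication use such as sedatives and neuromuscular blockade and/or alterations in metabolic function".

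The trigger adds to the difficulty. A significant imbalance becomes more likely the more treatment has changed use, which is when adjustment removes most. The reported quantity would then depend on an intermediate test result. VO₂ was the trial's first primary outcome and is still listed first among the secondary outcomes, so how its adjusted estimate is to be read matters.

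**Working it through.** **1. Which use is meant?** Two points favour on-treatment use. First, the general principles already deal with baseline imbalance, so a baseline-only reading makes the VO₂ sentence largely redundant. Second, the windows overlap. With the first dose at the latest permitted time, 12 h after ROSC, 48 − 12 = 36 of the 48 outcome hours follow it; an earlier dose gives more. Nothing restricts use to the period before that dose. This is an inference, because the timing is never stated.

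**2. The plan's own VO₂ figure.** Inputs from the sample-size section: difference 35 mL/min, SD 45 mL/min, power 0.8, α 0.05. Two-sided testing comes from the general principles ("All tests will be two-sided, a p-value <0.05 will be considered significant").

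n per arm = 2(1.960 + 0.842)² × 45² / 35² = 25.9, so 26. The t-test gives 26.9 (27). Dividing the normal figure by a Wilcoxon efficiency of 0.955 gives 27.2 (28). The plan states 28, so the figure reproduces. At the planned 30 per arm, t-test power is 0.84.

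**3. How often would the trigger fire?** The plan names no test; Fisher's exact test at 0.05 on any use (yes/no) is assumed. The probability is the sum, over all pairs of user counts, of the two binomial probabilities wherever Fisher p < 0.05. The documents give no usage rates, so all of these are assumed.

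| Use, placebo vs thiamine | Per arm | Trigger probability |
|---|---|---|
| 90% vs 90% | 30 | 0.9% |
| 80% vs 80% | 30 | 2.2% |
| 60% vs 60% | 30 | 2.6% |
| 80% vs 70% | 30 | 9% |
| 80% vs 60% | 30 | 30% |
| 80% vs 50% | 30 | 60% |
| 80% vs 50% | 25 | 51% |
| 80% vs 50% | 20 | 41% |
| 80% vs 50% | 15 | 25% |

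With no effect on use and two independent agents, the chance that at least one triggers runs from 1 − (1 − 0.009)² = 1.8% to 1 − (1 − 0.026)² = 5.1%. The smaller arm sizes matter because the note on the primary outcome reports that many patients did not meet the ventilator criteria for the first several hours, so fewer than 30 per arm may have usable data.

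**4. What would adjustment remove?** Suppose use shifts VO₂ by b and its prevalence is p₀ on placebo and p₁ on thiamine. Then total effect = direct effect + b(p₁ − p₀). With total 35, b = −30 and use 60% vs 30%, the direct effect is 35 − (−30)(0.30 − 0.60) = 35 − 9 = 26 mL/min. With 70% vs 30% it is 35 − 12 = 23.

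A simulation of the rule used 30 per arm, SD 45, 6,000 runs per row and one binary agent. It used a linear model with a t-test in place of quantile regression, on the mL/min scale of the sample-size section. The values of b and the usage rates are assumptions.

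| Use, placebo vs thiamine | b (mL/min) | Triggered | Mean estimate (total effect 35) | Power |
|---|---|---|---|---|
| 60% vs 60% | −30 | 3% | 35.0 | 84% |
| 60% vs 40% | −30 | 26% | 32.1 | 78% |
| 60% vs 30% | −30 | 55% | 28.4 | 65% |
| 70% vs 30% | −30 | 84% | 24.1 | 49% |
| 70% vs 30% | −45 | 83% | 18.6 | 36% |

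Without the conditional adjustment, the mean estimate stays at about 35 and power at about 84% in every row.

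**The case against.** The strongest reply is that the sentence may only apply the general baseline rule to two named agents. Then no mediator is involved. That reading cannot be excluded, but it leaves the adjustment hanging on a significance test. Between randomised arms any baseline imbalance is due to chance, and its p-value says little about whether the covariate is prognostic.

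Other points stand and limit the concern:

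- The Wilcoxon test takes no covariates, so an unadjusted result for VO₂, VCO₂ and RQ survives whatever happens. A reader might infer that the whole VO₂ result switches; only the quantile regression and the LQMM can. However, the plan does not say which result prevails, and the ratio analysis has no stated unadjusted counterpart.
- The consent section says eligible patients are already sedated. If use means any use, sedation can hardly differ between arms, and the trigger is mainly a matter for vasopressors unless dose or duration is counted.
- The documents give no evidence that thiamine changes the use of either agent. The attenuation figures need large assumed shifts, and the bias would reverse if use raised VO₂.
- Average temperature, apparently taken over the monitoring period, is always in the adjusted models and raises a similar question. Removing the clause does not make those models strictly total-effect models.

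A reader might also infer that the rule invalidates the type I error rate. No type I error was calculated, and with equal use the rule has almost no effect on the estimate or power, so that claim is not supported. Nor is it shown that the trigger fires whenever the drug works: it responds to agent use, not to VO₂.

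**Conclusion.** The concern holds in a limited form. The clause makes the covariates of the adjusted VO₂, VCO₂, RQ and VO₂:lactate models depend on a test of drug use whose timing, measure and method are undefined. On the likelier reading, it can turn a total effect into a partly mediated one when treatment changes use. On the baseline reading, it remains covariate selection by significance test.

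The size depends on assumptions that the documents cannot settle. If use does not change, the harm is negligible. Under a fall from 80% to 50%, the trigger would fire in about 60% of trials at 30 per arm and 41% at 20. In the illustrative 60% vs 30% case, the mean estimate falls from 35 to 28.4 mL/min and power from about 84% to 65%. These figures show direction and possible size; they are not forecasts. The issue concerns a secondary outcome. The primary lactate analysis is not touched by this sentence.

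**What to change.** 1. Delete the conditional clause, so that the sentence simply says vasopressor and sedation use are not controlled for.
2. Name the comparison without these covariates as the main VO₂ result. For VO₂, VCO₂ and RQ the planned Wilcoxon test already serves; for the ratio, state that the LQMM without them is the main model.
3. If adjustment is wanted, prespecify it on vasopressor use before the first dose, and on a pre-dose sedation measure that varies between patients (sedated or not would be nearly constant). Apply it whatever the observed imbalance.
4. Label any model containing on-treatment use as exploratory.

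The cost is a few sentences in the SAP, plus pre-dose data from the clinical record if item 3 is used. The document says it was submitted before unblinding or any analysis; the change should be made while that is still true. The small downside is that a chance imbalance in these agents would be addressed only in the prespecified or exploratory analysis.
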